7.3.2. Serious Adverse Events

All SAEs, regardless of causal relationship, that occurs after the subject first consents to participate in the study (ie, signing the informed consent) and throughout the duration of the study, including the 30 Day EOS Safety Follow-up period, must be reported to the eCRF database and Gilead PVE as instructed. This also includes any SAEs resulting from protocol-associated procedures performed after informed consent is signed.

If the investigator learns of any SAEs that occur after study participation has concluded and the event is deemed relevant to the use of IMP, he/she should promptly document and report the event to Gilead PVE.

Regarding subjects who prematurely discontinue study drug but remain on study, SAEs are collected as follows:

- Full Assessments (per Section 6.7.1): subjects continuing on study and completing full assessments, SAEs are collected throughout the duration of the study including the 30 Day EOS Safety Follow-up period.
- Limited Assessments (per Section 6.7.2): subjects continuing on study and completing limited assessments, SAEs are collected throughout the duration of the study including the 30 Day EOS Safety Follow-up period.
- Remote Assessments (per Section 6.7.3): subjects continuing on study and completing survival outcome assessments, SAEs are collected through the 30 Day EOT Follow-up period.

All AEs and SAEs will be recorded in the eCRF database within the timelines outlined in the eCRF completion guideline.

Electronic Serious Adverse Event (eSAE) Reporting Process

- Site personnel record all SAE data in the eCRF database and from there transmit the SAE information to Gilead PVE within 24 hours of the investigator's knowledge of the event. Detailed instructions can be found in the eCRF completion guidelines
- If for any reason it is not possible to record the SAE information electronically, ie, the eCRF database is not functioning, record the SAE on the paper serious adverse event reporting form and submit within 24 hours to:

Gilead PVE:

Fax: PPD

Email: PPD

- As soon as it is possible to do so, any SAE reported via paper must be transcribed into the eCRF database according to instructions and within timelines outlined in the eCRF completion guidelines
- If an SAE has been reported via a paper form because the eCRF database has been locked, no further action is necessary
- For fatal or life-threatening events, copies of hospital case reports, autopsy reports, and other documents are also to be submitted by e-mail or fax when requested and applicable. Transmission of such documents should occur without personal subject identification, maintaining the traceability of a document to the subject identifiers

- Additional information may be requested to ensure the timely completion of accurate safety reports
- Any medications necessary for treatment of the SAE must be recorded onto the concomitant medication section of the subject's eCRF and the event description section of the SAE form

7.4. Gilead Reporting Requirements

Depending on relevant local legislation or regulations, including the applicable US FDA Code of Federal Regulations, the EU Clinical Trials Directive (2001/20/EC) and relevant updates, and other country-specific legislation or regulations, Gilead may be required to expedite to worldwide regulatory agencies reports of SAEs, serious adverse drug reactions (SADRs), or SUSARs. In accordance with the EU Clinical Trials Directive (2001/20/EC), Gilead or a specified designee will notify worldwide regulatory agencies and the relevant IEC in concerned Member States of applicable SUSARs as outlined in current regulations.

In the intended study population, Gilead anticipates the occurrence of SAEs that would not be meaningful to report on an individual basis to regulatory agencies in an expedited fashion. These events include SAEs that are manifestations of the underlying disease, commonly occur in the study population independent of drug exposure, or are components of the study endpoints. The following SAEs will not be reported to regulatory agencies in an expedited fashion throughout the conduct of this clinical trial unless they are life-threatening or fatal, or if reporting is specifically requested by any regulatory agencies:

- Kidney impairment
- Chronic kidney disease
- Diabetic nephropathy
- Diabetes mellitus
- Hypertension
- Hyperkalaemia
- Hypoglycaemia
- Hyperglycaemia
- Blood creatinine abnormal
- Blood creatinine increased
- Glomerular filtration rate abnormal
- Glomerular filtration rate decreased

- Albuminuria
- Proteinuria
- Kidney failure
- End stage kidney disease
- Dialysis
- Dialysis device insertion
- Kidney transplant
- Acute myocardial infarction
- Cardiac failure congestive
- Cardiac failure acute
- Cerebrovascular accident
- Atrial fibrillation

Assessment of expectedness for SAEs will be determined by Gilead using reference safety information specified in the investigator's brochure or relevant local label as applicable.

All investigators will receive a safety letter notifying them of relevant SUSAR reports associated with any study drug. The investigator should notify the IRB or IEC of SUSAR reports as soon as is practical, where this is required by local regulatory agencies, and in accordance with the local institutional policy.

7.5. Toxicity Management

All clinical and clinically significant laboratory toxicities will be managed according to uniform guidelines detailed in the Management of Clinical and Laboratory Adverse Events ([Appendix 5](#)).

For study-specific discontinuation and interruption criteria, refer to Section [3.4](#) and Section [5.3.1](#). Specific toxicity discontinuation criteria in Section [3.4](#) supersede general toxicity guidelines, and in general, where discrepancy is present, the more conservative criteria apply. The Gilead Medical Monitor and/or sponsor designee should be consulted prior to study drug discontinuation when medically feasible.

7.5.1. Grades 1 and 2 Laboratory Abnormality or Clinical Event

For Grades 1 and 2 laboratory abnormalities or clinical events not specified in Sections [3.4](#) or Section [5.3.1](#), continue study drug at the discretion of the investigator.

7.5.2. Grade 3 Laboratory Abnormality or Clinical Event

For Grade 3 laboratory abnormalities or clinical events not specified in Sections 3.4 or Section 5.3.1, the following toxicity management guidelines apply:

- For a Grade 3 clinically significant laboratory abnormality or clinical event, study drug may be continued if the event is considered to be unrelated to study drug
- For a Grade 3 clinical event or clinically significant laboratory abnormality confirmed by repeat testing, that is considered to be related to study drug, study drug should be withheld until the toxicity returns to \leq Grade 2
- If a laboratory abnormality or clinical event recurs to \geq Grade 3 following re-challenge with study drug and is considered related to study drug, then study drug should be permanently discontinued and the subject managed according to local clinical practice. Recurrence of laboratory abnormalities considered unrelated to study drug may not require permanent discontinuation and study drug may be continued at the discretion of the investigator

7.5.3. Grade 4 Laboratory Abnormality or Clinical Event

For Grade 4 laboratory abnormalities or clinical events not specified in Sections 3.4 or 5.3.1, the following toxicity management guidelines apply:

- For a Grade 4 clinical event or clinically significant laboratory abnormality, confirmed by repeat testing, that is considered to be related to study drug, study drug should be permanently discontinued and the subject managed according to local practice. The subject should be followed as clinically indicated until the laboratory abnormality returns to baseline or is otherwise explained, whichever occurs first. A clinically significant Grade 4 laboratory abnormality that is not confirmed by repeat testing should be managed according to the algorithm for the new toxicity grade
- Study drug may be continued without dose interruption for a clinically non-significant Grade 4 laboratory abnormality (eg, Grade 4 creatine kinase after strenuous exercise or non-fasting triglyceride elevation that can be medically managed) or a clinical event considered unrelated to the study drug

Grade 4 treatment-emergent toxicities will be noted by the investigator and brought to the attention of the Gilead Medical Monitor and/or sponsor designee, who will discuss with the investigator and determine the appropriate course of action. All subjects experiencing AEs must be monitored periodically until symptoms subside, any abnormal laboratory values have resolved or returned to baseline levels or they are considered irreversible, or until there is a satisfactory explanation for the changes observed.

7.5.4. Liver Enzymes

To mitigate the potential risk of liver injury, subjects are monitored closely; defined rules for close observation and drug cessation due to elevated liver tests are specified.

After becoming aware of any of the following abnormal laboratory values, an unscheduled visit (ie, sequential visit) should occur to retest within 3 to 7 days of receipt of the original test results. Retest may be obtained sooner if medically indicated per investigator judgement.

If ALT and/or AST:

- > 3 – 5 x ULN (Grade 2): Monitor at least weekly until < or equal to 1.5 x ULN
- > 5 – 20 x ULN (Grade 3): Withhold study drug. Monitor at least weekly until ALT/AST are < or equal to 1.5 x ULN, then may resume study drug. If Grade 3 recurrence, withhold study drug. Monitor at least weekly until ALT/AST < or equal to 1.5 x ULN, then may resume study drug. If Grade 3 recurrence, discontinue study drug permanently
- > 20 x ULN (Grade 4): Withhold study drug until ALT/AST < or equal to 1.5 x ULN, then may resume study drug. If Grade 4 recurrence, discontinue study drug permanently

7.5.5. eGFR Decline

SEL is associated with an acute decline in eGFR after study drug initiation, and in the phase 2 study of SEL in DKD (GS-US-223-1015), the median acute eGFR decline associated with SEL 18 mg at Week 4 was 10%. We observed that approximately 25% of subjects had an acute eGFR decline of 19% or greater (25th percentile), and 75% of subjects had an acute eGFR decline of 4% or greater (75th percentile).

However, acute declines in eGFR are expected to occur in subjects with moderate to advanced DKD and may not necessarily be associated with SEL. If acute eGFR decline occurs after the period following study drug initiation, refer to the below instructions:

- If clinically indicated, evaluate for alternative etiologies of eGFR decline and address reversible factors
- Avoid withholding or discontinuation of study drug in the setting of eGFR decline to the extent possible
- Consult with Gilead Medical Monitor and/or sponsor designee prior to withholding or discontinuing study drug
- If study drug is withheld, restart study drug as soon as clinically appropriate and check eGFR at next scheduled visit, preferably with study drug taken for at least 7 consecutive days.

Additionally, progressive decline in kidney function is expected to occur in subjects with moderate to advanced DKD. SEL is hypothesized to slow progression of DKD, and study drug should not be discontinued in the setting of expected progressive decline of underlying kidney disease.

Specific toxicity interruption and discontinuation criteria listed above supersede general toxicity guidelines, and in general, where discrepancy is present, the more conservative criteria apply.

NOTE: During the time of the study drug interruption for any of the above, the subject may continue to have study visits and to take part in procedures and assessments, if deemed medically appropriate.

In addition, embryofetal toxicity was observed in SEL nonclinical studies; therefore to prevent potential fetal exposure, adherence to highly effective methods of contraception will be required. Please see [Appendix 6](#) for more details.

Any questions regarding toxicity management should be directed to the Gilead Medical Monitor and/or sponsor designee.

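### The ALT/AST rule in Protocol 7.5.4 permits study drug to resume where 7.5.2 and 7.5.3 require a permanent stop, and the protocol's precedence wording does not settle which governs

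*Protocol*

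**What the plan says.** Three sections of the protocol bear on stopping study drug for raised ALT/AST.

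- **7.5.4 (liver enzymes), Grade 4 (above 20 x ULN):** "Withhold study drug until ALT/AST < or equal to 1.5 x ULN, then may resume study drug", followed by "If Grade 4 recurrence, discontinue study drug permanently".
- **7.5.4, Grade 3 (above 5 and up to 20 x ULN):** withhold, and resumption is allowed after recovery. On return of the abnormality: "If Grade 3 recurrence, withhold study drug. Monitor at least weekly until ALT/AST < or equal to 1.5 x ULN, then may resume". On the next return: "If Grade 3 recurrence, discontinue study drug permanently". No step depends on whether the event is thought related to study drug.
- **7.5.3 (general Grade 4 rule):** for a laboratory abnormality that is clinically significant, confirmed on retest and "considered to be related to study drug, study drug should be permanently discontinued and the subject managed according to local practice".
- **7.5.2 (general Grade 3 rule):** for an abnormality that returns to Grade 3 or higher "following re-challenge with study drug and is considered related to study drug, then study drug should be permanently discontinued".

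Both general rules are limited to events that Sections 3.4 and 5.3.1 do not specify. The closing text of 7.5.5 then gives a tie-break: "Specific toxicity interruption and discontinuation criteria listed above supersede general toxicity guidelines, and in general, where discrepancy is present, the more conservative criteria apply". The opening of 7.5 has a sentence of similar build, but the specific criteria that it places above the general guidelines are those in Section 3.4.

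**The concern.** For the same severe liver event, one section instructs a permanent stop and another permits re-treatment. Protocol 1.6 and 7.5.4 both present the defined liver rules as the way in which potential liver injury is mitigated, so it should be possible to read off one answer for each situation. With about 190 centres planned, two sites could each follow a section of the protocol faithfully and act differently. A monitor could not say consistently which of them had deviated.

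The statistical stake is secondary. The stopping rule affects which subjects count as having discontinued study drug, and therefore the summaries of adverse events leading to discontinuation. It also affects the sensitivity analyses that drop off-treatment values or keep only subjects who completed treatment.

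**Working it through.** No sample size, error rate or event count enters this point. The check is to set the rules side by side and count the episode at which each requires a permanent stop, taking an event that meets the conditions of the general rule.

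| ALT/AST event | General rule | Liver rule (7.5.4) | Difference |
|---|---|---|---|
| Grade 4; clinically significant, confirmed, related | 1st episode (7.5.3) | 2nd episode | 2 − 1 = 1 |
| Grade 3; returns after re-challenge, related | 2nd episode, i.e. first recurrence (7.5.2) | 3rd episode, i.e. second recurrence | 3 − 2 = 1 |

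**Does the scope limit remove the conflict?** It would if 3.4 or 5.3.1 specified liver-enzyme events. Section 3.4 has no ALT/AST criterion, only judgement-based ones such as unacceptable toxicity or a clinically significant adverse event. Section 5.3.1 mentions liver enzymes, but only to send the reader to Section 7.5, and only for dose interruptions. Section 7.5 contains 7.5.2 and 7.5.3 as well as 7.5.4. The reference is therefore circular and says nothing about permanent discontinuation. Neither general rule names 7.5.4 as an exception.

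**Does the tie-break settle it?** Apply each clause of the 7.5.5 sentence to the two rows above.

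- Specific over general: 7.5.4 governs, so resumption is permitted.
- More conservative applies: 7.5.3 (Grade 4) or 7.5.2 (Grade 3 recurrence) governs, so the stop is permanent.

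The clauses disagree in both rows because, on permanent stopping, the specific rule is the less conservative one. The sentence does not rank them. The opening of 7.5 does not help: it gives precedence to Section 3.4, which is silent on ALT/AST.

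**Where the clauses agree.** For an unrelated Grade 3 elevation, 7.5.2 allows drug to continue and 7.5.4 withholds it. There the liver rule is both the specific and the stricter one, so either clause leads to 7.5.4. The conflict is confined to the two rows in the table.

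**A neighbouring gap.** Section 7.5.4 does not address mixed sequences (Grade 3 then Grade 4, or the reverse), whereas the recurrence wording of 7.5.2 would reach a return to Grade 3 or higher.

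The content of Appendix 5 is not available in the text reviewed beyond its reference to Section 7.5, so it cannot be used either way.

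**The case against.** The best reply is the scope limit. Section 5.3.1 names liver enzymes and eGFR decline, which are the subjects of 7.5.4 and 7.5.5. A natural reading is that these events leave the general rules and go to their own sections. That may well be what was intended. It is not what the text achieves, because 5.3.1 states no liver rule and covers interruptions only.

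Second, the tie-break can be read as ordered: the first clause is categorical and the second is softened by a general qualifier, so the specific rule would govern and the conservative default would cover the rest. This reading is available, but the sentence does not state it, and another careful reader could take the second clause as the answer to exactly this kind of discrepancy.

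Third, resumption under 7.5.4 is a permission. A site that stops permanently breaches neither section. This stands, but a site that uses the permission breaches 7.5.3 or 7.5.2, so the conflict remains.

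Fourth, a reader might infer that sites are left to decide alone. The documents do not support that. Under 5.3.1 the investigator should discuss the case with the Medical Monitor or sponsor designee before resuming drug. Under 7.5.3 the monitor takes part in deciding the course for Grade 4 toxicities. Section 7.5 asks for consultation before discontinuation when feasible. These steps reduce inconsistent handling materially. They do not remove it, since the monitor works from the same text.

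Finally, the liver rule is not laxer throughout. It withholds at Grade 3 whatever the suspected cause, and it sets recovery to 1.5 x ULN before resumption, where 7.5.2 accepts Grade 2 or lower.

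**Conclusion.** The ALT/AST stopping rules are internally inconsistent as written. The inconsistency is one episode wide at each of two grades, and the protocol's precedence wording does not resolve it.

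Two stronger conclusions should not be drawn.

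- A reader might infer that every related Grade 4 event and every related Grade 3 recurrence is affected. The Grade 4 conflict needs clinical significance and confirmation as well as relatedness. At Grade 3 only the first recurrence is in dispute, because by the second recurrence 7.5.4 also requires a permanent stop.
- A reader might infer that the primary result is at risk. SAP 6.1.3 defines a treatment-policy estimand that uses all observed values regardless of treatment discontinuation, so inconsistent stopping does not by itself remove a subject's observed data from the primary analysis. The effect there should be small. What remains falls mainly on the discontinuation summaries in SAP 7.1.6.3 and on the off-treatment and completer sensitivity analyses in SAP 6.1.3.

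That few such events will occur is an assumption; the documents give no expected frequency. The case for correction rests on the consequence of a single event and the low cost of the change.

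**What to change.** The sponsor's clinical team should reconcile 5.3.1, the opening of 7.5, 7.5.2, 7.5.3, 7.5.4 and the closing text of 7.5.5, so that one instruction applies to each ALT/AST grade and each recurrence, including mixed Grade 3 and Grade 4 sequences. The protocol should state which section governs. Two drafting devices would do this without prejudging the answer:

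- Name 7.5.4 explicitly as inside or outside the scope limits of 7.5.2 and 7.5.3.
- Put the two tie-break clauses in a stated order, and use the same sentence in 7.5 and 7.5.5.

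Which stopping or re-challenge rule is right is a clinical decision for the sponsor, and no view is taken on it here. The cost is protocol wording and a letter to sites. No change to the statistical analysis is needed.

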7.6. Special Situations Reports

7.6.1. Definitions of Special Situations

Special situation reports include all reports of medication error, abuse, misuse, overdose, reports of adverse events associated with product complaints, and pregnancy reports regardless of an associated AE and an AE in an infant following the potential exposure from breastfeeding and occupational exposure with an AE.

Medication error is any unintentional error in the prescribing, dispensing, or administration of a medicinal product while in the control of the health care provider, subject, or consumer.

Abuse is defined as persistent or sporadic intentional excessive use of a medicinal product by a subject.

Misuse is defined as any intentional and inappropriate use of a medicinal product that is not in accordance with the protocol instructions or the local prescribing information.

An overdose is defined as an accidental or intentional administration of a quantity of a medicinal product given per administration or cumulatively which is above the maximum recommended dose as per protocol or in the product labelling (as it applies to the daily dose of the subject in question). In cases of a discrepancy in drug accountability, overdose will be established only when it is clear that the subject has taken the excess dose(s). Overdose cannot be established when the subject cannot account for the discrepancy except in cases in which the investigator has reason to suspect that the subject has taken the additional dose(s).

Product complaint is defined as complaints arising from potential deviations in the manufacture, packaging, or distribution of the medicinal product.

Occupational exposure is defined as exposure to a medicinal product as a result of one's professional or non-professional occupation. Please refer to the Material Safety Sheet for product handling guidelines.

Infant exposure from breastfeeding that is associated with an AE is also considered a special situation report.

7.6.2. Instructions for Reporting Special Situations

7.6.2.1. Instructions for Reporting Pregnancies

The investigator should report pregnancies in female study subjects that are identified after initiation of study drug and throughout the study, including the post study drug follow-up period, to Gilead PVE using the pregnancy report form within 24 hours of becoming aware of the pregnancy.

Refer to Section 7.3 and the eCRF completion guidelines for full instructions on the mechanism of pregnancy reporting.

The pregnancy itself is not considered an AE nor is an induced elective abortion to terminate a pregnancy without medical reasons.

Any premature termination of pregnancy (eg, a spontaneous abortion, an induced therapeutic abortion due to complications or other medical reasons) must be reported within 24 hours as an SAE. The underlying medical reason for this procedure should be recorded as the AE term.

A spontaneous abortion is always considered to be an SAE and will be reported as described in Sections 7.1.1 and 7.1.2. Furthermore, any SAE occurring as an adverse pregnancy outcome post study must be reported to Gilead PVE.

The subject should receive appropriate monitoring and care until the conclusion of the pregnancy. The outcome should be reported to Gilead PVE using the pregnancy outcome report form. If the end of the pregnancy occurs after the study has been completed, the outcome should be reported directly to Gilead PVE. Gilead PVE contact information is as follows:

Email: PPD [REDACTED] and Fax: PPD [REDACTED]

Pregnancies of female partners of male study subjects exposed to Gilead or other study drugs must also be reported and relevant information should be submitted to Gilead PVE using the pregnancy and pregnancy outcome forms within 24 hours. Monitoring of the subject should continue until the conclusion of the pregnancy. If the end of the pregnancy occurs after the study has been completed, the outcome should be reported directly to Gilead PVE, fax number PPD [REDACTED] or email PPD [REDACTED]

Refer to Appendix 6 for Pregnancy Precautions, Definition for Female of Childbearing Potential, and Contraceptive Requirements.

